4. a. To assess if variability in physical therapy milestones post-op is associated with flare at 6 weeks
 - b. To assess if variability in physical therapy milestones post-op is associated with patient reported outcome measures at 1 year (for e.g., HAQ, DAS-28, HOOS, KOOS).
5. To evaluate if RA patients who flared within 6 weeks after arthroplasty exhibit an increase in ROCK activation at 6 weeks over and above pre-operative baseline levels, compared with patients who don't flare.
6. To better understand the molecular signature of RA flare and prodrome to RA flare. Blood samples harvested during various states of RA disease activity will be analyzed by RNA sequencing and Luminex® protein array to establish which pathways fluctuate most during disease worsening as well as prodrome to worsening. RA flare and the prodrome to flare will be measured by patient self-report using validated instruments of patient reported prodromal symptoms, patient reported disease activity measures and the OMERACT PFQs.

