3.0 What is/are the hypothesis(es)?

1. 26% of RA patients will flare after TJR, defined as
 - a. Post op increases in DAS28 > 1.2 if baselines < 3.2 or > 0.6 if baseline ≥ 3.2 OR
 - b. Are worse or much worse on question rating their RA since pre-surgery AND
 - c. Have at least one of
 - i. Want / need treatment
 - ii. An increase in MD Global of 2/10
 - iii. An increase in Patient Global of 2/10 (according to the definitions noted above)
2. The OMERACT preliminary flare questions (PFQs) will detect patients who flare as defined above.
3. RA patients who flare after TJR have worse baseline pre-operative disease activity (DAS >3.2), worse baseline function (HOOS, KOOS, HAQ, elbow/shoulder surveys) and more likely will have had a history of withdrawing a biological therapy compared to patients who do not flare.
4. RA patients who flare post op will not meet their physical therapy milestones and will have worse HOOS, KOOS, elbow, or shoulder pain and function outcomes 1 year after arthroplasty.
5. RA patients who flare will exhibit enhanced immune activation when baseline levels are compared to levels in patients who flare within 6 weeks of surgery based on increased expression/activation of ROCK, IRF4, IRF5 and IRF8 and decreased expression/activity of their inhibitors (Def6 and SWAP-70). These molecules participate in a biologic pathway that regulates production of pro-inflammatory cytokines, potential mediators of RA flare.
6. There is a discrete set of genes expressed in circulating monocytes in RA patients during flare and prodrome of flare.

4.0 Identify and define the primary outcome and when the outcome will be measured. If measuring change in post-operative function is the most important, that will be your primary outcome.

The primary outcome is rate of RA flare within 6 weeks of surgery as measured by the OMERACT flare questionnaire.

5.0 Identify and define the secondary outcome(s) and when they will be measured (list additional goals one at a time with their corresponding outcomes).

1. The severity and impact of flares, using the OMERACT PFQs in the post arthroplasty setting: PFQs including flare intensity, duration of flare and worsening of domains associated with flare (pain, fatigue, stiffness, patient

- reported tender and swollen joint count, difficulties with coping and participation).
- 2. DAS28 at baseline and post-op week 6, and the change during this interval.

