- 3. RAPID 3 weekly for 6 weeks and every 3 months for 1 year after arthroplasty, DAS-28, HOOS, KOOS, shoulder/elbow survey, patient global at baseline, 6 weeks, and 1 year.
- 4. Physical therapy functional milestones (PT questionnaire) at baseline and weekly for 86 weeks.
- 5. Biological markers of immune activation including levels of IRF4, IRF5, IRF8, IBP/Def6, SWAP-70, ROCK1, ROCK2 in synovial tissue taken at surgery. Levels of the same immune biomarkers in the peripheral blood measured pre-operatively, at 6 weeks post-operatively and at one year post-operatively.
- 6. Measurement of discrete set of genes expressed in circulating monocytes in RA patients obtained at baseline and weekly for 6 weeks after surgery in a subset of patients at high risk for flare (based on patients who withdrew biologics)

[Help](#)

ID: 2014-233

View: 2.1 Background

[Help](#)

BACKGROUND - Be sure to answer each question individually

1.0 Explain why these research questions are being asked:

RA patients who undergo arthroplasty have severe erosive disease; preliminary data suggests a flare rate as high as 26% in the post-operative period. This study would confirm the rate of post-operative flare, and evaluate the clinical and biologic factors which predict flare. We would also look at the impact of flare on arthroplasty outcomes (HOOS, KOOS, elbow/shoulder survey) and RA disease status (HAQ, DAS-28, RAPID) and better understand the biology of flare.

Flare after arthroplasty is clinically relevant, as medications are typically withheld at the time of surgery with the aim of diminishing surgical site infections.

However, patients who flare may not be able to adhere to post-operative rehabilitation regimens, leading to worse functional outcomes. In addition, patients who flare may have difficulty achieving remission or low disease activity when medications are re-started, leading to worse disease outcomes. There is little information about the characteristics and outcome of flare in the post-operative period. Better understanding of the incidence and clinical characteristics of post-operative flare and the means to predict who will be most likely to flare could lead to more tailored management strategies and potentially better arthroplasty and disease outcomes.

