Collecting specimens longitudinally from a cohort of well characterized RA patients with high likelihood of worsening disease activity and post-operative flare provides a unique opportunity to study the biology of RA worsening in the context of clinical domains associated with RA disease activity and flare. It is well known that deregulation of immune responses plays a major role in many autoimmune diseases like RA. Delineating the molecular mechanisms which control the development, activation and differentiation of immune cells could lead to better understanding of how they become deregulated in disease states including RA, with particular focus on a set of molecules that are important in controlling the activation of immune cells. These molecules include IRF4, IRF5, IRF8, IBP/Def6, SWAP-70, ROCK1, ROCK2, and signaling molecules involved in responsiveness to activation stimuli. We hypothesize that in those RA patients who flare after arthroplasty there will be increased ROCK activation leading to enhanced activity of IRF4 (as well as IRF8 and possibly IRF5) and increased expression of pro-inflammatory cytokines/chemokines such as IL-17, IL-21 and CCL20. By following the levels to of ROCK pathway molecules longitudinally we can determine the relationship of these molecules to states of disease activity.

Patients managed with TNF inhibitors who discontinue the medication provide a unique opportunity to study the biology of flare in RA. An unbiased, bioinformatics approach to patient assessment is a useful strategy for identifying defects in complex pathways that result in RA disease activity. Transcriptomes from purified populations of peripheral blood mononuclear cells (CD4+, CD8+, CD20+, CD14+, CD56+) will be compared from samples harvested from patients who flared to those who did not flare during follow up.

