Many patients with RA who flare describe non-specific prodromal symptoms such as intense fatigue and flu-like symptoms. These may represent manifestations of a cytokine storm that is triggered by unknown antecedents. Instruments to measure flare such as the OMERACT PFQs have been very recently developed and validated to provide a new opportunity to correlate molecular findings with clinical signs and symptoms of flare. Patients managed with TNF inhibitors who discontinue the medication perioperatively are most likely to be at increased risk for flare and provide a unique opportunity to study the biology of flare in RA. The goal of this aim is to correlate the clinical phenotype as measured by the OMERACT PFQ, measured weekly with the immunological data. The immunological phenotype will be characterized using RNA sequencing of white blood cell (WBC) to develop a comprehensive molecular profile of RA flare.

Comparison of data collected in patients who flare versus those who do not flare provides a unique opportunity to characterize and understand flare, and define the significance of perioperative flare on arthroplasty and disease outcomes while providing further understanding of the biology and immunology of RA worsening.

2. Pincus T, Sokka T, Kautiainen H. Patients seen for standard rheumatoid arthritis care have significantly better articular, radiographic, laboratory, and functional

status in 2000 than in 1985. *Arthritis Rheum* 2005; Apr;52(4):1009-19.

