In aim 5 and 6 we will compare levels of serum and tissue biomarkers between RA who flare and RA who do not flare using T-tests or chi-square tests, as appropriate. We will correlate self-report functional scores and biomarkers with the development of flare using Spearman correlations.

After sequencing, the reads will be processed by the New York Genome Center in a dedicated RNA-Seq pipeline, consisting of ribosomal RNA filtering, genome mapping with STAR, various QC metrics obtained with picard tools and transcript quantification with HTSeq-count. The raw read counts will then be processed with one of the Bioconductor package for Differential Gene expression (DESeq, edgeR, or limma/voom).

[Help](#)

ID: 2014-233

View: 2.4 Consent Information

[Help](#)

Consent Information

1.0 Describe how, when, and where the consent process will be initiated:

If possible, before coming in to the hospital (either for a pre-operative visit or their surgery), patients will be called by a research team member to discuss the study and evaluate their interest in participating. Patients who are interested will then be consented prior to surgery by the study research assistant or their treating surgeon, or rheumatologist either in the office, in pre-surgical screening, or in the pre-op holding area. If convenient, patients can additionally review the study protocol with the coordinator over the phone, but they will always be consented in person. The consent will be placed in the patients' hospital chart.

In the event that a potential participant requires a translator and is scheduled to have surgery on a weekend, a co-investigator of the research study can contact the potential participant prior to the day of their surgery and consent the patient over the phone. The Hospital for Special Surgery's Language Services Phone Interpreter or in-house employee will translate the Informed Consent to Participate in a Research Study Involving Genetic Testing, the Short Form Consent, and the Research Authorization Form. The translator would function as the witness to the consenting process. If the participant agrees to enroll, the participant will sign these forms in person on the day of their first study visit.

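### Aim 6 asks what changes in blood gene expression as a patient enters prodrome and flare, but the only blood contrast stated is flarers against non-flarers, which cannot separate that change from stable differences between patients

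*Combined protocol and SAP*

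**What the plan says.** **The question.** Aim 6 (Specific Aims, item 2.0) is meant "to establish which pathways fluctuate most during disease worsening as well as prodrome to worsening". Its material is described this way: "Blood samples harvested during various states of RA disease activity will be analyzed by RNA sequencing". Hypothesis 6 (item 3.0) reads "There is a discrete set of genes expressed in circulating monocytes in RA patients during flare and prodrome of flare". Secondary outcome 6 (item 5.0) plans monocyte samples "obtained at baseline and weekly for 6 weeks after surgery in a subset of patients at high risk for flare", the subset being patients who withdrew biologics. Background, item 2.0, adds: "The goal of this aim is to correlate the clinical phenotype as measured by the OMERACT PFQ, measured weekly with the immunological data".

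**The comparison.** The same Background item says that transcriptomes of purified blood cell populations "will be compared from samples harvested from patients who flared to those who did not flare during follow up". In Data Analysis (2.11.1, item 3.0), the paragraph for aims 5 and 6 says "we will compare levels of serum and tissue biomarkers between RA who flare and RA who do not flare using T-tests or chi-square tests", and adds Spearman correlation with development of flare. On sequencing it says only "The raw read counts will then be processed with one of the Bioconductor package for Differential Gene expression", listing DESeq, edgeR and limma/voom. It gives no contrast, design matrix or false discovery rate. The section declares all secondary outcomes exploratory.

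**The concern.** Whether a pathway fluctuates as a patient worsens is a question about change within a patient. Whether flarers differ from non-flarers is a question about two kinds of patient. The answers agree only if the two kinds of patient would have had equal expression in the absence of flare.

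The protocol does not expect that. Hypothesis 3 predicts worse pre-operative disease activity and worse baseline function in flarers. A gene linked to long-standing severity would then differ at every draw, including before any flare, and could enter the signature. A gene that does rise at flare could be hidden if the stable difference runs the other way. Such a list would send follow-up work after markers of who flares while presenting them as markers of flaring. Prodrome, the other half of the aim, has no stated contrast.

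**Working it through.** **The plan's own figure.** Aim 6 has no sample size, effect size or error rate to reproduce. The only figure available for scale is the primary one: an exact two-sided binomial test of 0.26 against 0.10 with N = 47. Rejecting at 6 or fewer or 19 or more flares gives power 0.8143 and alpha 0.0445, as printed. Expected flarers are 0.26 × 47 = 12.2, so 12 against 35 is used below.

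**Assumptions, none in the documents for aim 6.** One gene has total SD 1 at a draw and within-patient correlation ρ. Alpha is 0.05 two-sided per gene. S is the stable flarer minus non-flarer difference, F the change at flare, and T a post-operative shift common to everyone. The between-patient test is taken on flare-time samples; the plan does not say which samples enter.

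**(a) Flarers against non-flarers at the flare draw.** The expected difference is S + F. Noncentrality = (S + F)/√(1/12 + 1/35) = (S + F)/0.3345, on 45 df. ρ does not enter.

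**(b) Flare minus own baseline, flarers only.** The expected value is F + T, with SD √(2(1 − ρ)). Noncentrality = (F + T)√12/√(2(1 − ρ)), on 11 df.

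**(c) Flarers' change against non-flarers' change.** The expected difference is F; S and T cancel. Noncentrality = F/(0.3345 √(2(1 − ρ))), on 45 df.

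**Gene that does not change at flare (F = 0)**

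| S | noncentrality in (a) | flagged by (a) | flagged by (c) |
|---|---|---|---|
| 0.5 | 0.5/0.3345 = 1.49 | 31% | 5% |
| 0.8 | 0.8/0.3345 = 2.39 | 65% | 5% |
| 1.0 | 1.0/0.3345 = 2.99 | 83% | 5% |

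Simulation with 20,000 replicates at S = 0.5 and 1.0 agrees: (a) gives 31% and 83% at ρ = 0.5, 0.7 and 0.9, and (c) stays at about 5%.

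**Gene that rises 0.7 SD at flare (F = 0.7, S = 0)**

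| ρ | SD of change | power (a) | power (c) |
|---|---|---|---|
| 0.3 | 1.18 | 53.5% | 41% |
| 0.5 | 1.00 | 53.5% | 53.5% |
| 0.7 | 0.77 | 53.5% | 75% |

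With an opposing stable difference, S = −0.5, the net difference in (a) is 0.2. Noncentrality is 0.60 and power 9%. Power for (c) is unchanged.

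**Why (b) is not the remedy.** With F = 0, T = 0.5 and ρ = 0.7, noncentrality is 0.5 × 3.464/0.775 = 2.24, and (b) rejects about 53% of the time with no flare effect at all. Contrasts (a) and (c) stay at 5%.

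**Sensitivity to subset size.** The aim 6 subset is smaller than 47 and of unstated size. With 6 against 12, taken only as an example, (a) flags the unchanged gene in about 16% (S = 0.5) to 47% (S = 1.0). That is less often, but still well above 5%.

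**Are the samples there?** Secondary outcome 6 plans baseline and weekly draws. Interventions and Observations (2.6) and Data Collection (2.7) describe study blood at surgery, 6 weeks and 1 year, plus an optional draw if the patient is hospitalised. Neither describes a weekly draw. In the directory listing (View 9.45), the extra eligibility criteria for aim 6 are struck through.

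**The case against.** The strongest reply is that the plan leaves the model open; it does not choose a wrong one. The flarer against non-flarer sentence stands in Background, the t-test sentence speaks of biomarker levels and not read counts, and the sequencing paragraph states no contrast. Sampling by disease state, weekly draws and the goal of correlating weekly flare questions with immunological data all point towards a longitudinal analysis.

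Much of that stands. A reader might infer that the investigators have ruled out a patient term or decided to throw away the pre-operative sample. The documents say neither. Part of the laboratory text on blood in Data Collection is also unreadable in the copy reviewed, so a statement there may be lost. But the analysis section is legible, and the correlation goal is not carried into it. The only groups it names for aim 6 are flarers and non-flarers.

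Three further points are right. Biologic withdrawal, also named in Hypothesis 3, is largely fixed by how the subset is defined, so the argument rests on disease activity and function. The 12 and 35 come from the primary sample size, and genome-wide calls are not made at 0.05 per gene, so the percentages are illustrative. Flarers against non-flarers is a proper comparison where the question is prediction, as for synovium sampled once at surgery.

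**Conclusion.** The concern holds in limited form. As written, the blood contrast cannot tell stable patient differences from change at flare, and either can be reported as the flare signature. It does not follow that the list would contain only stable differences: the contrast mixes the two.

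Under the stated assumptions, an unchanged gene with a stable difference of 0.5 to 1.0 SD is flagged in about 31% to 83% of runs, against about 5% for change against change. This does not depend on the within-patient correlation. It does depend on group sizes and on the stable difference, which are assumed.

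A reader might also infer that the present contrast always costs power. It does not. For a 0.7 SD rise, change against change gains at correlation 0.7 (about 75% against 53%), ties at 0.5 and loses below that. The case for it is bias, not power. It assumes that surgery and time would move flarers and non-flarers alike in the absence of flare.

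Because the aim is exploratory, the consequence lies in how the signature is read and which candidates go forward. The primary flare-rate estimate is untouched.

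**What to change.** For the blood RNA-seq, state the following in Data Analysis:

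1. Label each sample by the patient's measured state at that draw (neither flare nor prodrome, prodrome, flare), with the definitions fixed in advance. Do not assume that a pre-operative sample is stable.
2. Fit edgeR or limma/voom with patient as a block and terms for draw time. Alternatively use limma's duplicateCorrelation, keeping the group term in the model so that the stable difference is absorbed.
3. Make the state/time-by-group contrast primary for aim 6: flarers' change into the state against non-flarers' change over matched draws. Do not use a flarers-only paired test. State the false discovery rate.
4. Report flared against not flared on pre-operative blood separately, as a predictor analysis. Leave the synovial comparison as it is.
5. Reconcile the weekly draws in secondary outcome 6 with the surgery, 6-week and 1-year draws in 2.6 and 2.7. Baseline and 6-week samples support the flare contrast for patients in flare at week 6. Prodrome needs the weekly samples; if they are not taken, drop the prodrome claim.

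The cost is analysis-plan wording and a different design matrix in packages already named, with no new draws for the flare contrast. The price is some power for genes with low within-patient correlation. Weekly sampling is a real cost only if it is not already in place.

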If 26% of RA patients flare in the post-operative period then it would be important to know if these patients have differences in achieving successful outcomes from their arthroplasty surgery both in the short and long term and it would then be important to know what can be done to modify flares. It will also be important to identify predictors of these flares as these might be modifiable risk factors or signaling biomarkers. Validation of these would require a larger study. An understanding of the disease pathogenesis assessed when tissue specimens as

well as serum biomarkers are studied in the perioperative context may also contribute the identification of biomarkers associated with flare. In addition, if biologic precursors and predictors of flare are identified, they could have additional applicability in RA management.

5.0 Is this a pilot study that could lead to a more definitive protocol or different study? ☐ Yes ☒ No

5.1 If you answered No, please explain below:

This is not a pilot study.

6.0 Please upload reference or additional document here (if needed).

Name	Description
There are no items to display	

[Help](#)

ID: 2014-233

View: 2.2 Study Design

[Help](#)

Study Design

1.0 Observational:

Name	Description
Prospective Cohort Study	A prospective evaluation of a cohort of patients with a specific characteristic over time to see if they develop a particular endpoint or outcome based on a stated hypothesis (e.g., establishing a cohort to follow patients undergoing a novel procedure in order to evaluate pre- and post-operative function/pain). These studies are conceived before data is collected.

2.0 Experimental:

Name	Description
There are no items to display	

2.1 If Other, please specify:

2.2 If Randomized Controlled Clinical Trial is selected, please choose one of the following:

Name
There are no items to display

If other, please list name or indicate N/A below:

ID: 2014-233

View: 2.3 Recruitment

[Help](#)

Recruitment

1.0

Check all that apply to describe your study population:

Population

Patients

Vulnerable Populations

There are no items to display

1.1 If Other, please specify:

2.0 Inclusion Criteria: *list characteristics that potential subjects and controls need to have. Use a bullet format, if applicable.*

1. Age > 18

2. Patients with Rheumatoid Arthritis, Osteoarthritis, or Inflammatory Arthritis undergoing **primary total hip replacement surgery, primary total knee replacement surgery, primary total elbow replacement surgery or primary total shoulder replacement surgery**

3. Satisfy ACR/EULAR 2010 classification criteria and/or the 1987 RA criteria (see below) and be diagnosed with RA (unless IA patient or OA control).

Rheumatoid arthritis 1987 criteria:

1. morning stiffness in and around joints lasting at least 1 hour before maximal improvement;
2. soft tissue swelling (arthritis) of 3 or more joint areas observed by a physician;
3. swelling (arthritis) of the proximal interphalangeal, metacarpophalangeal, or wrist joints;
4. symmetric swelling (arthritis);
5. rheumatoid nodules;
6. the presence of rheumatoid factor; and
7. radiographic erosions and/or periarticular osteopenia in hand and/or wrist joints.

*Criteria 1 through 4 must have been present for at least 6 weeks. Rheumatoid arthritis is defined by the presence of 4 or more criteria, and no further qualifications (classic, definite, or probable) or list of exclusions are required.

ACR/EULAR 2010 criteria for the classification of RA:

Table 3. The 2010 American College of Rheumatology/European League Against Rheumatism classification criteria for rheumatoid arthritis

Target population (Who should be tested?): Patients who

- 1) have at least 1 joint with definite clinical synovitis (swelling)*
- 2) with the synovitis not better explained by another disease

Classification criteria for RA (score-based algorithm: add score of categories A-D;

a score of $\geq 6/10$ is needed for classification of a patient as having definite RA

Score

A. Joint involvement

0	1 large joint	
	2-10 large joints	1
	1-3 small joints (with or without involvement of large joints)	2
	4-10 small joints (with or without involvement of large joints)	3
	>10 joints (at least 1 small joint)	5

B. Serology (at least 1 test result is needed for classification)

0	Negative RF and negative ACPA	
	Low-positive RF or low-positive ACPA	2
3	High-positive RF or high-positive ACPA	

C. Acute-phase reactants (at least 1 test result is needed for classification)

0	Normal CRP and normal ESR
1	Abnormal CRP or abnormal ESR

D. Duration of symptoms

0	< 6 weeks
1	≥ 6 weeks

*The criteria are aimed at classification of newly presenting patients. In addition, patients with erosive disease typical of rheumatoid arthritis (RA) with a history compatible with prior fulfillment of the 2010 criteria should be classified as having RA. Patients with longstanding disease, including those whose disease is inactive (with or without treatment) who, based on retrospectively available data, have previously fulfilled the 2010 criteria should be classified as having RA.

3.0

Exclusion Criteria: *list characteristics that would cause you to exclude potential subjects and controls.*

Justify any age, ethnicity, language, or gender-based exclusion criteria. *Use a bullet format, if applicable.*

1. Primary diagnosis of any of the following systemic rheumatic diseases (see ICD-9 codes 135.0, 136.1, 274, 279.4, 279.8, 287.0, 446.0, 446.1, 446.2, 446.21, 446.4, 446.7, 447.6, 556, 710.0, 710.2, 710.8, 710.9, 711.1, 711.2, 713.3, 713.7, 716.2, 719.3, 720.1, 725)
2. Diagnosis of or crystalline arthropathy.
3. Unable to understand or read English.
4. Unable to follow the study protocol in a reliable manner.
5. Age < 18.

4.0 Age Range:

>18

5.0 Describe how you will identify and recruit potential subjects for participation in the study.

A Recruitment Flyer will be placed in the dictation cubbies and exam rooms of participating surgeons. If a patient with a possible or previous diagnosis of RA schedules an arthroplasty, members of the surgeon's office will send the patient information to the Research Staff using either the study e-mail address, [contact], or other secure forms of communication. Patients will be identified pre-operatively by their treating surgeon or identified by screening patients' records prior to their pre-operative visit.

Patients will be called prior to coming in to the hospital either for their pre-surgical screening visit or for their surgery, depending on when they were identified as a potential subject. A research assistant/ research team member will describe the study, discuss any questions the patient may have, and evaluate the patient's interest in participating in the study. If the patient is interested in the study, they will then be met in person at their visit to the hospital (pre-surgical screening visit or on their day of surgery) to discuss the study further and be consented.

They will receive a Study Overview Sheet (see attached) either in the office, in the mail, or on the day of surgery. They will have the opportunity to discuss any questions with the research assistant/ research team member who will ensure they meet study criteria (see screening sheet). In addition, patients may be identified and recruited from the Total Joint Replacement Patient Education Class by the research assistant. Finally, research assistants may use PS Reporter, MMF, or Clinstar to identify patients before their pre-surgical screening visit, or prior to their surgical procedure. We will request an IRB approved Waiver of HIPAA Authorization.

6.0 * Please select enrollment type from following drop down list:

Over Course of Study

[Help](#)

ID: 2014-233

View: 2.3 Target Enrollment

[Help](#)

Target Enrollment

- 1.0 * What is the maximum number of subject you plan to enroll in this study at HSS?(Please enter a number)
200
- 2.0 If this is a multi-center study, indicate the projected total subject accrual across all sites.

[Help](#)

ID: 2014-233

View: 2.35 Patient Subjects

[Help](#)

Patients

1.0 Please check the box(es) below that best reflect how patients will be identified and recruited for participation.

How subjects will be identified

- ☒ Potential subjects will be identified after a review of medical records of patients under the care of one or more of the study investigators
- ☒ Medical records and/or other Institution sources (databases, registries, billing records, pathology reports, admission logs) will be reviewed to identify potential participants. May involve access of records by individuals not involved in the patient's care.
- ☒ Potential subjects will be identified by their treating physicians and referred to the researchers. Patients' private and identifiable information will not be shared prior to receiving permission from the patient to do so.
- ☐ Potential subjects will be identified from a registry of individuals interested in research opportunities.
- ☐ Subjects will roll-over from another research study.
- ☐ Potential subjects will self-refer in response to advertisements.

ID: 2014-233

View: 2.6 Interventions and Observations

[Help](#)

Interventions and Observations

1.0 Be specific and describe the Interventions or Observations that will be part of this research project. Include a detailed description of the treatment arms, if applicable.

Clinical Data:

If willing to participate, the RC will complete a study screening form, obtain consent, complete a Research Authorization Form and the patient will complete a pre-operative questionnaire/survey containing questions about their demographic information (race, ethnicity, age, weight), medical history, assessment of their replaced joint function, and symptoms as they relate to their RA (OA and IA patients will not be asked survey questions that apply only to RA patients). We requested an IRB approved Waiver of HIPAA Authorization.

o The questionnaire will include patient demographics, RA characteristics, co-morbid conditions, disease classification, medications, PtGA, SF-12, HAQ, RAPID, joint count homunculus, HOOS/KOOS/elbow/shoulder survey.

The research staff will complete a second survey that will ask about the participant's medical history, and medication history.

o The questionnaire will include Medications, disease duration and classification criteria, assessment for extra-articular disease and co-morbidities, MDGA, DAS28, CDAI

~~OA and IA~~ Patients: We will repeat both questionnaires at 6 weeks after surgery at the time of the participants' regularly scheduled appointment.

RA Patients only:

- We will repeat both questionnaires at 6 weeks and one year after surgery at the time of participants' regularly scheduled appointments.
- Questions about RA will also be asked by telephone or by e-mailing an electronic survey each week for six weeks, and then every three months for the rest of the year.

o The questionnaire will include OMERACT flare questions, RAPID, joint humunculus

All questionnaires can be completed in any of the following ways throughout the course of the study: in person at the hospital, over the phone, via e-mail using a secure survey, or by mailing paper forms to and from the hospital.

Blood sample:

We would like to collect and store serum from participants in this study, which means we will need to increase our day-of-surgery allowed blood draw limit from 50.5 to 56.6mL (well below the IRB cap of 550mL):

- **30mL** whole blood in green top heparin tubes (3 tubes, 10mL each, for PBMC isolation)
- **8.5mL** speckle top tube (1 tube, to be spun by research assistant and aliquotted for freezing at -80)
- **2.5mL** for PAXgene tubes (1 tube, to be frozen by the research assistant)
- If not ordered at Pre-Surgical Screening, **3mL** lavender top for erythrocyte sedimentation rate (as marker of inflammatory levels)
- If not ordered at Pre-Surgical Screening, **5mL** into gold serum separator tube for c-reactive protein levels (as marker of inflammatory levels)
- If not available in medical record, **10mL** for combined Rheumatoid Factor (RF) and Anti-Citrullinated Protein Antibody (ACPA, also known as anti-CCP)
- *We will no longer be collecting PAX gene tubes day-of-surgery, which were 2.5mL each*

$30 + 8.5 + 2.5 + 3 + 5 + 10 = 59 \text{ mL}$, which is 3.99 tablespoons

IA and RA patients only:

For follow-up visits, we would like to add serum collection, in addition to the whole blood we are already collecting. We would like to increase our 6-week follow-up and 1-year follow-up visit blood draw limit from 28mL to 36.5mL (well below the IRB cap of 550mL):

- **20mL** whole blood in green top heparin tube (2 tubes, 10mL each, for PBMC isolation)
- **8.5mL** speckle top tube (1 tube, to be spun by research assistant and aliquotted for freezing at -80)
- If not ordered by treating physician, **3mL** lavender top for erythrocyte sedimentation rate (as marker of inflammatory levels)
- If not ordered by treating physician, **5mL** into gold serum separator tube for c-reactive protein levels (as marker of inflammatory levels)

$20 + 8.5 + 3 + 5 = 36.5 \text{ mL}$, which is 2.47 tablespoons

- All: In the event that a participant is hospitalized at Hospital for Special Surgery or one of its affiliates at any time between their enrollment on the day of surgery and their 6-week follow-up appointment with their surgeon, we may ask for an additional blood draw of 2 tablespoons (20 ccs) of blood to take place at the time of their routine morning blood draw.
- If for any reason routine lab work is not required at the participants' study visits, we would still require 2 tubes of blood for study purposes and would make arrangements to do so. All samples will be de-identified.
- If for any reason subjects are unable to provide blood at their 6-week or 1-year follow-ups (for example, if the subject was too busy, the line at phlebotomy was too long, or the subject simply did not schedule a 1-year follow-up), we will contact the subject and ask them if they would like to have the blood drawn by Apex Laboratory, Inc, a mobile laboratory capable of visiting patients to draw blood in their homes. If they express interest, we will sent them a new informed consent form, cover letter, and prepaid return envelope. When we recieve the signed consent form, we will call the subject to coordinate an Apex Laboratory visit date. Apex will call the patient to coordinate the proper time to arrive, and will draw a maximum of 1.5 tablespoons of blood for ESR and CRP blood tests. The results of these tests will be communicated to the study research assistant through Apex's HIPAA-compliant web-based platform.

Surgical sample:

- During surgery, the subjects' surgeon will take samples of the tissue removed as part of their surgery from their joint. Specifically for THR, the femoral head will be collected intra-operatively from standardized anatomic sites, (fovea and capsular reflection). For TKR, tissue samples of the patella cartilage, distal femur and proximal tibia, and synovium from the suprapatellar pouch will be collected intra-operatively.
- We collect and analyze this tissue to learn more about the cellular activity that occurs with RA flare. Tissue will be processed first in pathology: sample saved in OCT and 2 slides stained with H&E. Slides will be scored according to a modified Scanzello scoring system. Synovial tissue and PBMCs will be processed according the standard operating procedures established by the AMP network. Cellular samples will be analyzed at HSS, and shared with the AMP network for additional specialized technical analytics to explore markers and pathways expressed in tissue and cells, using (but not limited to) those being explored in the AMP network such as RNA-Seq, ATAC-Seq, CyTOF, FACS.
- We will also photograph the specimen using the Pathology Lab equipment. This photograph will be de-identified before it is used for research purposes. We will also capture de-identified microscopy images of H&E slides prepared from these samples.

